#### 2. Implant Dosimetry And Treatment Planning And Dosage Recommendations

Optimization of dosimetry is performed that creates the optimal disease coverage. Packing can be used to stabilize the geometry. The target is to treat Point A to 80-85 Gy for early stage disease and 85-90 Gy for advanced disease. The dose constraints are to limit the bladder dose to the LDR equivalent of 80 Gy and the rectal dose below 75 Gy.

## **B. Endometrial Cancer**

### **1. Technique**

Participants eligible for the protocol shall have definitive adjuvant radiotherapy or be treated because they are deemed to have inoperable disease or are poor surgical candidates. In some cases this regimen may be changed to fit the individual needs and requirements of each participant and the number of external beam and brachytherapy treatments may be slightly different. These slight differences will be discussed with the participants prior to the beginning of therapy and if necessary during therapy as well. The radiation therapy for this study is considered the “standard of care” of the treatment of endometrial cancer.

Technical aspects that should be considered for endometrial participants in brachytherapy: a rectal tube should be placed, the largest vaginal cylinder possible should be used and 2/3 of the vaginal cuff should be targeted.

### **2. Implant Dosimetry And Treatment Planning And Dosage Recommendations**

Suggested doses of HDR alone to be used for adjuvant treatment of postop are as follows:

No. of HDR fractions	HDR dose/fx	Dose-specific point	Equiv. dose for tumor effects	Equiv. dose (late effects with DRF)
3	7.0	0.5-cm depth	29.8	23.2
4	5.5	0.5-cm depth	28.4	21.1
5	4.7	0.5-cm depth	28.8	20.7
2*	16.2*	Vaginal surface	70.7	65.0
3	10.5	Vaginal surface	53.8	45.6
4	8.8	Vaginal surface	55.1	45.1
5	7.5	Vaginal surface	54.7	43.3

Suggested doses of EBRT and HDR to be used for adjuvant treatment of postop endometrial cancer are as follows:

EBRT (Gy) @ 1.8 Gy/fx	No. of HDR fractions	HDR dose/fx	Dose-specific point	Equiv. dose for tumor effects	Equiv. dose (late effects with DRF)
45	2	5.5	0.5-cm depth	58.5	53.7
45	3	4.0	0.5-cm depth	58.3	52.9
45	2	8.0	Vaginal surface	68.3	62.5
45	3	6.0	Vaginal surface	68.3	61.3

The ABS recommends that the proximal 3–5 cm of the vagina be treated; however if a characteristic of the participant presentation dictates that more or less of the vagina should be treated, then this detail is left to the discretion of the investigator. For serous and clear cell histologies, treatment of the entire vaginal canal should be considered. The dose distribution should be optimized to deliver the prescribed dose either at the vaginal surface or at 0.5-cm depth. The physician should be mindful that when then vaginal recurrence is at the distal vaginal cuff, the entire vagina and the inguinal nodes should be considered for treatment.

In those cases in which HDR only for treatment of inoperable primary endometrial cancer

No. of HDR fractions	HDR dose/fx*	Equiv. dose for tumor effects	Equiv. dose (late effects with DRF)
4	8.5 Gy at 2 cm	52.4	42.6
5	7.3 Gy at 2 cm	52.6	41.4
6	6.4 Gy at 2 cm	52.5	40.3
7	5.7 Gy at 2 cm	52.2	39.0

In those participants cases in which external beam + HDR is needed for treatment of inoperable primary endometrial cancer, the following schedule should be adhered to:

EBRT (Gy) @ 1.8 Gy/fx	No. of HDR fractions	HDR dose/fx	Equiv. dose for tumor effects	Equiv. dose (late effects with DRF)
45	2	8.5 Gy at 2 cm	70.5	64.5
45	3	6.3 Gy at 2 cm	69.9	62.8
45	4	5.2 Gy at 2 cm	70.6	62.5

In participants with vaginal cuff recurrences, the following doses can be considered:

EBRT (Gy) @ 1.8 Gy/fx	No. of HDR fractions	HDR dose/fx	Dose-specification point	Equiv. dose for tumor effects	Equiv. dose (late effects with DR)
45	3	7.0	0.5-cm depth	74.0	66.4
45	4	6.0	0.5-cm depth	76.3	67.4
45	5	6.0	Vaginal surface	84.3	73.4
45	4	7.0	Vaginal surface	83.9	74.2

ICRU reference points should be localized and calculated, respecting normal tissue tolerance as noted above.

The dose should be limited as follows: the upper vaginal mucosa should receive no more than 150 Gy, the lower vaginal mucosa should receive between 80-90 Gy and the rectal point dose should be less than 70 Gy, the bladder point should be less than 75 Gy. (12)

## C. Lung Carcinoma

### 1. Technique

A flexible nylon catheter will be introduced through the bronchoscope into the lumen and is positioned at least 2 cm beyond the visible tumor. The prescription point should prescribe the radiation dose at 10mm from the center of the catheter. A margin of at least 1-2 cm beyond the disease is recommended.

### 2. Implant Dosimetry And Treatment Planning And Dosage Recommendations

The ABS recommends for those participants who are undergoing palliative brachytherapy only, 3 weekly fractions of 7.5 Gy each, 2 fractions of 10 Gy each or 4 fractions of 6 Gy each.

For participants with curative intent, the recommendations are as follows: as a boost to external beam radiation therapy, 3 fractions of 5 Gy each or 2 fractions of 7.5 Gy each. If it is used alone in participants who have not received radiotherapy, 5 fractions of 5 Gy each or 3 fractions of 7.5 Gy each prescribed to 1 cm can be considered.

The plan will be optimized and treatment delivered. (8)

## **D. Breast**

### **1. Technique**

Planning target volume is the lumpectomy site with 1-2 cm margin as clinically indicated. The CTV = PTV and the prescription dose must encompass the target volume and the dose will be prescribed to 1 cm from the applicator surface.

### **2. Implant Dosimetry And Treatment Planning And Dosage Recommendations**

A minimum of 7mm between the skin and balloon should be maintained. During the planning process, normal tissue doses will be respected and a three-dimensional calculation with DVH-based analysis should be created. Breast dose parameters should include V100, V150, and V200. Skin dose parameters should include Dmax. (6)

- Target coverage:  $\geq 90\%$  of the dose delivered to  $\geq 90\%$  of the target volume
- V150: balloon catheter  $< 50 \text{ cm}^3$
- V200: balloon catheter  $< 10 \text{ cm}^3$
- DHI  $\geq 0.75$  where DHI =  $(1 - V150/V100)$
- Maximum skin isodose: balloon catheter  $< 145\%$
- Primary treatment 34 Gy in 10 fractions over 5 treatment days

If treatment is being delivered as the primary treatment then it should be given as 34 Gy in 10 fractions over 5 days. Treatment should be administered either before or after chemotherapy (if persistent cavity or surgical clips placed). If chemotherapy will be administered, then the recommendation is to wait  $>2$  weeks after completion of APBI before initiating (6)

## **E. Prostate**

### **1. Technique and dosage recommendations**

Definitive boost therapy: For definitive boost therapy, a single HDR brachytherapy implant (1500 cGy/implant) will be delivered within 21 days of a course of external beam radiotherapy (4600 cGy, 2Gy/day or 4500 cGy, 1.8 Gy/day). Alternative fractionation schedules include 9.5 Gy- 11.5 Gy x 2 fractions, 5.5-7.5 Gy x 3, and 4.0-6.0 Gy x 4 fractions. These regimens are those described in the ABS and NCCN guidelines.

Definitive monotherapy: The regimen chosen will be based on participant and tumor factors. For definitive monotherapy, doses of 12-13.5 Gy x 2 fractions, 9.5 Gy x 4, 10.5 Gy x 3 are described by the NCCN and ABS as appropriate monotherapy doses and will be options for treatment on this protocol.

Salvage: For salvage, participants will receive 8 Gy x 4 fractions without external beam irradiation.

Simulation: Participants will undergo CT simulation for the external beam portion of treatment as per routine in the supine position. For EBRT the planning target volume (PTV) will be defined as the clinical target volume (CTV) plus a margin defined by the treating physician. The external beam component will be delivered in one phase. Treatment planning goals are to try to achieve an isodose distribution where the PTV is covered by at least the 90% isodose line, and the 100% isodose line encompasses the CTV. Doses will be prescribed to the 100% isodose line.

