Breast HDR brachytherapy provides a potential benefit to woman who may suffer from diminished cosmesis as a results of their larger breast size or those who are unable to travel the long distances daily for a conventional 6-week course of external radiation therapy. (6)

Prostate HDR has a long history in the radiation oncology branch in which there was significant accrual to the previous “phase II study of MR-guided high dose rate brachytherapy boosts for prostate cancer”. Guidelines from this study represent a natural extension of the protocol that we are completing here. In general, clinical evidence has shown that dose escalation in organ confined prostate cancer improves local disease control (13, 14). HDR brachytherapy represents an elegant method of accomplishing dose escalation in prostate cancer (15) but precise evidence guiding dose and fractionation is lacking (16). HDR brachytherapy has three potentially significant roles in the curative intent treatment of prostate cancer: 1) as a boost in conjunction with supplemental EBRT for intermediate and high risk prostate cancer and 2) as monotherapy in low and low intermediate risk prostate cancer and 3) as salvage for localized recurrence after prior external beam irradiation or radical prostatectomy. The use of HDR brachytherapy as a boost as per 1) has significant evidence for the ability to dose escalate by way of hypofractionation with excellent biochemical relapse-free survival rates with a low incidence of severe late genitourinary or gastrointestinal toxicities (16,17) and this has been formalized in the NCCN guidelines. The use of HDR brachytherapy as monotherapy is supported by data from several institutions (18,19) and a recent systematic review (20). Prostate-specific antigen progression-free survival using monotherapy ranged from 79% to 100% and local control from 97% to 100% with low toxicity rates. The use of HDR brachytherapy for localized recurrence while an exciting prospect remains investigational. As a whole, high dose rate brachytherapy is technically complicated but increasingly practiced in the United States with significant heterogeneity in terms of the doses and fractionations being employed. HDR for various body sites has so many advantages over low-dose rate or simple external radiation therapy which include but is not limited to: faster treatment times on an outpatient basis resulting in less resources utilized on the participant and hospital’s behalf, better optimization secondary to the ability to vary dwell time versus low-dose rate therapy and a sharp dose fall-off allowing for decreased dose to adjacent critical organs

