## **2 ELIGIBILITY ASSESSMENT AND ENROLLMENT**

### **2.1 ELIGIBILITY CRITERIA**

#### **2.1.1 Inclusion Criteria**

- 2.1.1.1 Pathologically confirmed malignancy for which high-dose rate brachytherapy is appropriate as a component of their therapeutic regimen.
- 2.1.1.2 Age  $\geq$  18 years of age.
- 2.1.1.3 ECOG performance status of 0, 1, or 2 (see [Appendix B](#))
- 2.1.1.4 Participant must have a primary medical or surgical oncologist in the community or at NCI who is willing to collaborate with the ROB staff in the clinical management of the participant.
- 2.1.1.5 Participants of childbearing or child- fathering potential must be willing to use a medically acceptable form of birth control, which includes abstinence, while they are being treated on this study.
- 2.1.1.6 Site-specific inclusion criteria (any one or more of the following):
  - 2.1.1.6.1 Gynecologic cancers
    - 2.1.1.6.1.1 Endometrial cancer
      - Participants at a higher risk of recurrence (because of either grade, myometrial invasion, lymphatic vascular space invasion, tumor size, lymph node status, tumor extension, presence or absence of surgical staging)
      - Participants who have suffered a recurrence at the vaginal cuff
      - Participants who are unable to undergo surgery and must have treatment for an inoperable primary endometrial cancer.
    - 2.1.1.6.1.2 Cervical cancer
      - Participants who are unable to undergo surgery and must have treatment for an inoperable primary cervical cancer.
      - Participants with locally advanced cervical cancer in whom brachytherapy will be integrated as a boost to external beam radiation either a palliative or curative setting (definitive or post-operative setting).
    - 2.1.1.6.1.3 Lung cancer
      - Participants with an endobronchial component causing symptoms
      - Participants who cannot undergo resection because of poor lung function or distant lung metastasis
    - 2.1.1.6.1.4 Breast cancer
      - Infiltrating ductal carcinoma or DCIS, stage T0, T1, and T2  $\leq$  3.0 cm, N0 and M0,

- Participants benefiting from HDR as either as a boost or accelerated partial breast irradiation regimen.

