#### 2.1.1.6.4 Prostate Cancer

- Participants with localized prostate cancer (T1b-T3b) in whom brachytherapy will be integrated as a boost to external beam radiation or used as monotherapy for definitive management.

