### 4.2 CONCURRENT THERAPIES

No investigational drugs or therapies will be administered by NCI ROB personnel in this protocol. However, the participant may be receiving other appropriate cancer therapy based on standard practice. This will be coordinated by the referring oncologist.

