## **8 HUMAN SUBJECTS PROTECTIONS**

### **8.1 RATIONALE FOR SUBJECT SELECTION**

Participants will be invited to enroll onto this trial if they are an adult and meet the eligibility criteria outlined in section [2.1](#). No gender, racial or ethnic groups will be excluded from participation in this trial. Adults who are cognitively impaired prior to study entry will not be eligible for study entry because they cannot give informed consent.

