### **8.3 EVALUATION OF BENEFITS AND RISKS/DISCOMFORTS**

All procedures/tests in this protocol are used routinely in standard care settings with minimal associated risks and/or discomforts. Participants on this study will be receiving treatment for their malignancy per standard of care. There are no direct medical benefits expected from taking part in this study. We hope the information learned from this study will benefit participants in the future.

The risks and benefits of each procedure/test, as well as the implications of the procedure/test results will be discussed thoroughly with the participant prior to the intervention. Specific risks and potential complications of each procedure will be outlined in a consent form. When the procedure/test poses any risk to the participant, an additional consent will be obtained.

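### Appendix A gives a dose and a target for salvage prostate brachytherapy, but the prostate inclusion criterion does not name salvage and section 8.3 describes all treatment as standard of care

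*Combined protocol and SAP*

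**What the plan says.** **Treatment.** Appendix A, E. Prostate, part 1 sets out definitive boost, definitive monotherapy and then a third entry: "Salvage: For salvage, participants will receive 8 Gy x 4 fractions without external beam irradiation". Part 2 adds that the salvage volume covers the suspected recurrence.

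**Eligibility.** Section 8.1 ties enrolment to section 2.1: "Participants will be invited to enroll onto this trial if they are an adult and meet the eligibility criteria outlined in section" 2.1. The prostate criterion, 2.1.1.6.4, admits localized disease, T1b to T3b, "in whom brachytherapy will be integrated as a boost to external beam radiation or used as monotherapy for definitive management". The prostate exclusions in 2.1.2.9.2 are distant and nodal metastases only.

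**Status of salvage.** Section 1.2.2 gives HDR three roles in prostate cancer, the third being "as salvage for localized recurrence after prior external beam irradiation or radical prostatectomy". It then says: "The use of HDR brachytherapy for localized recurrence while an exciting prospect remains investigational".

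**Risk description.** Section 8.3 says: "Participants on this study will be receiving treatment for their malignancy per standard of care". Section 4.2, under the heading on concurrent therapies, says: "No investigational drugs or therapies will be administered by NCI ROB personnel in this protocol".

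**The concern.** A man with a local recurrence after radiotherapy or prostatectomy has a regimen waiting for him in Appendix A, but no line in section 2.1 clearly lets him in and no exclusion keeps him out. Two investigators could decide differently and each cite the protocol.

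If he is enrolled, the general statement in 8.3 describes as standard of care a use that the background calls investigational. Some of these men will have had earlier pelvic irradiation, and the radiation risks in 8.3.1 do not mention re-treatment. At stake are who may be enrolled and whether the IRB has an accurate account of what they will receive.

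**Working it through.** The plan states no figure for this point, so the check is mainly a comparison of text.

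**1. Is salvage meant to be given?** It appears three times: as a role in 1.2.2, as a dose in Appendix A.E part 1 and as a target in part 2. The dose sentence is directive, although the appendix title calls its doses suggested. This looks deliberate rather than a leftover phrase.

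**2. Does 2.1.1.6.4 cover it?** The criterion names boost and definitive monotherapy. Section 1.2.2 numbers salvage separately from both, and Appendix A.E gives it its own entry after definitive monotherapy. For endometrial cancer, recurrence is a listed route: "Participants who have suffered a recurrence at the vaginal cuff". On the plan's own vocabulary, then, salvage is a third category that the prostate criterion leaves out.

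**3. Does the risk section fit?** For a salvage participant, the statement in 1.2.2 that the use is investigational and the statement in 8.3 that treatment is standard of care cannot both hold.

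**4. Does the target definition fit?** Appendix A.E part 2 requires the clinical target volume to include the prostate gland as a minimum, and then adds the recurrence for salvage. After radical prostatectomy there is no gland to include.

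**5. Does the primary decision change?** The section 7 rules depend only on counts and on p0 = 0.65 and p1 = 0.90. The chance of acceptance is the sum over x = 7 to 9 of P(X1 = x) × P(X2 ≥ 23 − x), with X1 binomial on 9 and X2 binomial on 19. This gives 0.0340 at p = 0.65 (stated below 0.04) and 0.910 at p = 0.90, so beta is 0.090 (stated below 0.10). None of these inputs refers to salvage. Cohort 4 in 2.3.1 is defined by a prostate cancer diagnosis, so a salvage participant counts in the prostate 28 by default.

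**6. Is the salvage course itself unusually intense?** The late-effect column of the endometrial tables in Appendix A.B is reproduced by n·x·(x + 3)/5, where x is 0.7 times the dose per fraction:
- 3 × 7.0 Gy: x = 4.9, giving 3 × 4.9 × 7.9/5 = 23.2, as tabulated.
- 4 × 5.5 Gy: x = 3.85, giving 4 × 3.85 × 6.85/5 = 21.1, as tabulated.

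Applying it to prostate is an assumption. The second column drops the 0.7 factor, for tissue at full prescription dose.

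| Regimen (Appendix A.E) | With factor 0.7 | Without |
|---|---|---|
| Salvage, 8 Gy × 4 | 4 × 5.6 × 8.6/5 = 38.5 | 32 × 11/5 = 70.4 |
| Monotherapy, 12 Gy × 2 (lowest) | 2 × 8.4 × 11.4/5 = 38.3 | 24 × 15/5 = 72.0 |
| Monotherapy, 9.5 Gy × 4 (highest) | 4 × 6.65 × 9.65/5 = 51.3 | 38 × 12.5/5 = 95.0 |

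Taken alone, salvage lies at the low end of the admitted monotherapy range, or just below it.

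**The case against.** **Salvage may already be eligible.** It is HDR alone, section 1.2.2 places all three roles under curative intent, and no prostate exclusion mentions recurrence or prior radiation. Silence is not exclusion elsewhere either: 1.2.2 describes lung brachytherapy after maximal earlier irradiation, yet the lung criteria do not mention it. This stands far enough that one cannot say section 2.1 bars salvage outright. It does not remove the problem. If salvage is eligible, the clash between 1.2.2 and 8.3 applies to real participants; if it is not, Appendix A directs treatment for people who cannot enrol.

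**Section 4.2 concerns other treatment.** Its heading and the sentences that follow are about therapy given alongside HDR. A reader might infer that 4.2 flatly promises that no salvage will be given, but the context does not support that. Its sentence does reach therapies given by branch staff within the protocol, so it is secondary support only. The conflict with 8.3 does not need it.

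**The salvage dose has a source.** A reader might infer that it has none, because the boost and monotherapy entries name ABS or NCCN and the salvage entry does not. But all of Appendix A is headed as following ABS guidelines, and part E closes with citations. Whether these cover 8 Gy × 4 cannot be checked from the documents.

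**Missing safeguards are not peculiar to salvage.** Numeric urethra and rectum limits are given only for the 15 Gy boost, so every other prostate schedule lacks them too. The plan says constraints vary with fractionation, and it requires organ contours and dose-volume histograms, individual assessment (3.2.1) and exclusion where safe ABS-conforming treatment is not possible (2.1.2.8). This objection stands: prior-dose, interval and organ limits are clinical choices, not corrections of an error.

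**Conclusion.** The concern holds as an inconsistency. Appendix A.E directs a salvage treatment that 2.1.1.6.4 does not name, and 8.3 describes as standard of care a use that 1.2.2 calls investigational. It should be corrected because it governs who may be enrolled and how re-treatment is described to the IRB.

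Its size is limited. The 7 of 9 and 23 of 28 rules and the maximum accrual of 28 per stratum and 112 overall are untouched. The documents give no basis for saying how many salvage participants there would be, or whether their implants would meet the coverage criterion more or less often.

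A reader might also infer that salvage exposes men to far more radiation than any admitted regimen. The documents do not support a figure. They state no prior external beam dose, and any excess would rest on an assumed prior dose, full overlap in the same tissue and no recovery. The salvage course alone is not high, and a man treated after prostatectomy may have had no earlier radiation at all.

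The conclusion rests on reading salvage as distinct from definitive monotherapy, as 1.2.2 and Appendix A.E both present it. The consent form was not available, so its risk wording is not judged.

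**What to change.** Make section 2.1 and Appendix A.E agree.

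**If salvage is intended**, which the three mentions suggest:
- name local recurrence after prior external beam irradiation or prostatectomy in 2.1.1.6.4;
- qualify 8.3, and 4.2 with it, so that salvage is not described as standard of care;
- add the risk of re-irradiation to 8.3.1;
- state in Appendix A.E part 2 that after prostatectomy the recurrence volume replaces the whole-gland minimum.

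Section 7 could add one sentence confirming that these participants count in the prostate 28.

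**If salvage is not intended**, delete the salvage dose sentence and the salvage target sentence in Appendix A.E.

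Whether to add prior-dose, interval or organ-limit criteria is for the sponsor's clinical judgement.

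The first route costs a handful of wording changes, the second two deletions. Both need IRB review as an amendment. Neither adds participants or alters the design.
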